## 2.3 Sample size

This trial is powered with regard to the difference between intervention 1 (GUT.EXPECT+SC) versus the control condition (SC). Based on the literature reviewed, we assume a within-group standard deviation (SD) of 75 points on the irritable bowel syndrome severity scoring system (IBS-SSS). Given this SD, a difference of 40 points on the IBS-SSS can be detected with a power of 80%, using a two-sided alpha of 5%, by including 29 patients per group, yielding a total sample size of n=87 for UC and IBS, respectively. Based on the results of our prospective cohort study, we assume a loss to follow-up between baseline and the primary outcome measurement (ie, 3 months follow-up) of 25%, resulting in a total of n=117 randomised patients for UC and IBS, respectively. Assuming that 50% of patients with UC or IBS will meet the inclusion criteria, n=234 patients per diagnostic group will be assessed for eligibility.

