## 5.2 Analysis methods

### 5.2.1 Primary outcome

An analysis of covariance will be used to investigate the group differences in the IBS-SSS, adjusted for baseline IBS-SSS. The underlying disease (UC vs IBS) and sex will be added as additional factors. Assuming no interaction effect between disease and treatment group, this is more effective than analysing both disease conditions independently. If the overall comparison yields a significant F-statistic, pairwise comparisons can be performed without adjustment of the type 1 error because of the closure testing principle. This analysis will be performed using the FAS. In the case of significant F-statistic, we will report baseline adjusted means and their respective differences, including 95% confidence intervals.

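### The 80% power in SAP 2.3 is for a direct test of GUT.EXPECT versus SC, but 5.2.1 opens that contrast, and commits to reporting it, only after a significant three-arm F test

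*SAP*

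**What the plan says.** SAP section 2.3 names one contrast: "This trial is powered with regard to the difference between intervention 1 (GUT.EXPECT+SC) versus the control condition (SC" (GUT.EXPECT plus standard care against standard care alone). It assumes a within-group SD of 75 IBS-SSS points and says that a difference of 40 points "can be detected with a power of 80%, using a two-sided alpha of 5%, by including 29 patients per group". This gives 87 evaluable patients in each disease and, with 25% loss, 117 randomised in each. The section mentions neither an overall test nor an expected GUT.SUPPORT result.

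SAP section 5.2.1 analyses UC and IBS together in one ANCOVA of IBS-SSS with baseline IBS-SSS, disease and sex. Its decision rule is: "If the overall comparison yields a significant F-statistic, pairwise comparisons can be performed without adjustment of the type 1 error". The justification given is the closure principle. On reporting it says: "In the case of significant F-statistic, we will report baseline adjusted means and their respective differences", with 95% confidence intervals. Section 3.1 sets the two-sided 5% level for all tests. No section lets the powered contrast be tested outside the F test.

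**The concern.** The power statement and the decision rule describe different procedures. A direct test of one contrast succeeds when that contrast is significant. The rule in 5.2.1 also requires the 2-degree-of-freedom F test to be significant, so its power for the same contrast cannot be higher and is usually lower. It also depends on where the GUT.SUPPORT mean falls, which 2.3 does not consider.

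Two things are at stake. A GUT.EXPECT benefit over SC could be significant on the contrast the trial was powered for and still not be claimable. And if the F test is not significant, the SAP contains no commitment to report the adjusted estimate of the primary effect or its confidence interval, which is when readers most need the interval.

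**Working it through.** **Inputs.** From SAP 2.3: difference 40, SD 75, two-sided 5%, 29 evaluable per arm in each disease. From 2.2: allocation 1:1:1. From 5.2.1: both diseases in one model, so n = 2 × 29 = 58 per arm and 174 in all. Residual degrees of freedom are 174 − 6 = 168 (three arms, baseline, disease, sex). The GUT.SUPPORT mean is not given, so it is varied.

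**1. Reproduce the stated figure.** n per arm = 2 × (1.96 + 0.84)² × 75² / 40² ≈ 55.2, so 56 (57 with the exact t test). Two times 29 gives 58. Power at 58: standard error 75 × √(2/58) = 13.93, noncentrality 40/13.93 = 2.87, power 81.9% (normal) or about 81.4% (noncentral t). The stated 80% is therefore reproduced for the direct test, with the diseases pooled. For losses, 87/0.75 = 116, against 117 stated.

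**2. Power of the F test alone.** Noncentrality λ = n Σ(μᵢ − μ̄)²/SD², with critical F(2, 168) = 3.05.
- GUT.SUPPORT equal to SC or to GUT.EXPECT: Σ = 1066.7, λ = 58 × 1066.7/5625 = 11.0, power 84.6%.
- GUT.SUPPORT midway: Σ = 800, λ = 58 × 800/5625 = 8.25, power 72.3%.

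**3. Power of the rule in 5.2.1** (F significant and GUT.EXPECT versus SC significant in the right direction; simulation with at least 400,000 runs per case):

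| GUT.SUPPORT mean | Direct test | F test, then contrast |
|---|---|---|
| Equal to SC or to GUT.EXPECT | 81% | 77% |
| A quarter of the way from either | 81% | 73% |
| Midway | 81% | 71% |

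In the midway case about one in eight of the trials with a significant direct contrast fail the F test.

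**4. The same point on the IBS-SSS scale.** With an observed SD of 75, the direct test needs an observed difference of 1.974 × 13.93 = 27.5 points. If the observed GUT.SUPPORT mean is midway, F = n d²/(4 SD²), so F > 3.05 needs d > 75 × √(4 × 3.05/58) = 34.4 points. A difference between 27.5 and 34.4 would be significant on the powered contrast but not claimable.

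**5. What brings the two-step rule back to 80%.**
- GUT.SUPPORT 10 points worse than SC or 10 points better than GUT.EXPECT: 80%. At 5 points outside, 79%.
- If 75 is an unadjusted SD and the baseline to 3-month correlation is ρ, the residual SD is 75 × √(1 − ρ²). Power reaches 80% at ρ ≈ 0.24 (SD 72.8) with GUT.SUPPORT at either end, and at ρ ≈ 0.42 (SD 68.1) midway. At an assumed ρ of 0.5 (SD 65.0) it is 84% to 89%, against 91% direct.
- With neither, 62 evaluable per arm are needed (ends) up to 70 (midway): 3 × 62/0.75 = 248 to 3 × 70/0.75 = 280 randomised, against 234 planned.

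**6. Cost of a fixed order instead.** Suppose the order is GUT.EXPECT versus SC, then GUT.EXPECT versus GUT.SUPPORT, then GUT.SUPPORT versus SC, each only if the previous one succeeds. Same inputs:
- GUT.EXPECT versus SC: about 81% whatever the GUT.SUPPORT mean.
- GUT.SUPPORT versus SC: from about 77% under the SAP rule to about 1% if GUT.SUPPORT equals GUT.EXPECT (2% if the middle step may be significant in either direction), and from about 29% to 3% midway.
- GUT.EXPECT versus GUT.SUPPORT, if GUT.SUPPORT equals SC: from 77% to 71%.

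**The case against.** The F test followed by unadjusted pairwise tests is a valid closed procedure for three arms. It also treats the three contrasts alike, which suits section 2.1: the design is meant to separate the targeted effect from general effects and to compare the experimental interventions with no intervention. This stands. Type I error is not at issue, and keeping the F test is defensible.

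A reader might infer that the trial cannot reach 80% power under its own rule. The documents do not support that. Section 5.2.1 adjusts for baseline, and 2.3 does not say whether 75 is a raw, change or adjusted SD. If it is raw, a moderate correlation restores 80%. If it is already adjusted, this defence fails. The SAP does not settle which, and 2.3 takes no credit for the adjustment.

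A reader might also take 71% as the expected figure, on the view that a supportive arm will naturally fall in between. The SAP states no expected GUT.SUPPORT effect, so midway is one case among several. At either end the shortfall against 80% is under 3 points.

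Finally, section 2.2 describes randomisation in the past tense, so restating the power is unlikely to change the sample size. That limits the practical effect, but not the case for a correct statement. None of these objections touches the conditional reporting.

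**Conclusion.** The mismatch between 2.3 and 5.2.1 is real. The 80% describes a direct test that the SAP does not perform. Under the stated SD and difference, pooled over the diseases and without credit for baseline adjustment, the rule that the SAP does apply has 71% to 77% power for GUT.EXPECT versus SC when the GUT.SUPPORT mean lies anywhere from SC to GUT.EXPECT. This is a loss of about 4 to 10 points against the direct test. Whether true power is below 80% depends on the GUT.SUPPORT mean and the residual SD, which the SAP leaves open.

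The reporting weakness depends on no such assumption: the commitment to give adjusted means, differences and intervals is tied to a significant F. Both points should be corrected. Neither affects the validity of the tests.

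**What to change.** 1. **Section 5.2.1:** report the baseline-adjusted means and all three pairwise differences with 95% confidence intervals whatever the F result. The F test then decides only which differences may be claimed as significant. This costs one sentence.
2. **Section 2.3:** restate the power for the two-step rule as 71% to 77% under SD 75 and a difference of 40. Name the GUT.SUPPORT mean assumed (77% at SC or GUT.EXPECT, 71% midway), and say that the figure is pooled over UC and IBS and takes no credit for baseline adjustment. The only cost is a less favourable number. If the sponsor wants credit for the adjustment, the SAP should say what kind of SD 75 is and state the correlation assumed.
3. **Option, not a requirement:** test GUT.EXPECT versus SC first, directly at two-sided 5%, which restores about 81%. If the strict three-step order follows, the SAP must state that it nearly removes the power for GUT.SUPPORT versus SC (about 77% to 1% if GUT.SUPPORT equals GUT.EXPECT). Any such change should be made before the outcome data are seen by arm.

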## 1.2 Objectives

Since both factors can potentially be modified by targeted interventions, this study will investigate defined mechanisms of action; namely, whether persistent gastrointestinal symptoms in UC and IBS can be influenced by modifying dysfunctional symptom expectations and illness-related anxiety. Studying a primarily inflammatory and a primarily functional bowel disease in parallel allows for the investigation of whether the same mechanisms of symptom persistence are involved for these two different, yet related diseases.

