### 5.2.2 Secondary outcomes

The secondary outcomes will be reported according to their respective scale.

Group differences of PHQ-15, SSCAI, C-reactive protein, and faecal calprotectin will also be analysed using analysis of covariance with underlying disease (UC vs IBS) and sex as additional factors. The same reasoning as for the primary outcome IBS-SSS applies.

All variables will be checked for skewness and if necessary appropriately transformed.

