#### 5.4.2 Subgroup analysis

Exploratory subgroup analyses aim at identifying subgroups which may especially benefit or do not respond well to the treatment groups offered, as measured by the reduction in gastrointestinal symptom severity (IBS-SSS). For this purpose, an ANCOVA for the IBS-SSS at 3 months as dependent variable will be performed in the ITT population, adjusted for the IBS-SSS at baseline and including group allocation as factor and the interaction between group and specified interaction variable. For each defined interaction variable, a separate ANCOVA model will be examined.

Interaction test p-values and. Subgroup-specific means and pairwise effect differences with 95% confidence intervals will be reported in the case of interaction tests with p values of less than 0.15 in accordance with the EMA guideline on the investigation of subgroups in confirmatory clinical trials. The presented p-values will not be adjusted for multiple comparisons.

The following subgroup variables will be investigated in separate ANCOVA models regarding their potential interaction with the intervention groups with respect to the change in the IBS-SSS from baseline to 3 months:

*Key subgroups*

- Diagnosis (UC vs. IBS)
- Gender (female vs. male; diverse patients are excluded for this analysis)

*Exploratory subgroups*

- Age (young [ $\leq$ first tercile] vs. middle aged vs. old [ $>$ third tercile])
- Migration background (none vs. 2nd generation [mother and/or father not born in Germany] vs. 1st generation [patient not born in Germany])
- Education ( $\leq$  10 years in school vs.  $>$  10 years in school)
- Duration of symptoms in years ( $<$ 5 years vs 5-10 years vs  $>$ 10 years)
- Baseline IBS-SSS none [0-74] vs mild [ $\geq$ 75-174] vs moderate [ $\geq$ 175 - 300] vs severe [ $>$ 300] ( this analysis will not be adjusted for baseline IBS-SSS)
- Somatic symptom severity (PHQ-15 categorical:  $<$ 10 vs  $\geq$ 10)
- Somatosensory Amplification (SSAS split at median ( $\leq$ 15 vs  $>$  15))
- PHQ-15 categorical:  $<$ 10 vs  $\geq$ 10)
- GAD-7 categorical:  $<$ 10 vs  $\geq$ 10
- TAS-20 as 20-60 vs  $\geq$  61
- ERQ suppression split at median ( $\leq$ 3.25 vs  $>$  3.25)
- SSD-12  $<$  24 vs  $\geq$  24
- Adverse childhood events (ACE-D: 0 vs. 1-3 vs.  $\geq$  4)
- BMI ( $<$  18,5 vs.  $\geq$  18,5 to 24,9 vs.  $\geq$  25)

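### The SAP commits to reporting the primary treatment estimates and confidence intervals only in the case of a significant overall F test

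*SAP*

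**What the plan says.** Section 5.2.1 specifies an analysis of covariance of the IBS-SSS across three arms, adjusted for baseline IBS-SSS, disease and sex. It then sets two conditions on the overall F test.

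- Testing: "If the overall comparison yields a significant F-statistic, pairwise comparisons can be performed without adjustment of the type 1 error because of the closure testing".
- Reporting: "In the case of significant F-statistic, we will report baseline adjusted means and their respective differences, including 95% confidence intervals".

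Section 3.1 fixes the level and sidedness of whatever confidence intervals are presented, but does not say which must be presented. Section 5.2.2 uses the same type of model for PHQ-15, the colitis activity index, C-reactive protein and faecal calprotectin, and adds: "The same reasoning as for the primary outcome IBS-SSS applies". Whether the reporting condition carries over to these outcomes is left open.

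Section 5.4.2 has a similar rule for subgroups. Subgroup means and pairwise differences with intervals "will be reported in the case of interaction tests with p values of less than 0.15". Diagnosis (UC or IBS) is the first of the two key subgroups. The primary model pools the diseases on this argument: "Assuming no interaction effect between disease and treatment group, this is more effective than analysing both disease conditions independently".

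**The concern.** The two conditions in section 5.2.1 do different jobs. The testing condition is sound: with three arms, a significant global test followed by unadjusted pairwise tests is a valid closed procedure. The reporting condition does not follow from it. Showing a difference with its confidence interval rejects no hypothesis, so it cannot affect the type 1 error.

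Two things are at stake. First, after a non-significant F the plan does not oblige anyone to show the effect of GUT.EXPECT versus standard care. Readers then cannot tell a result that rules out the 40-point target from one that is merely imprecise. Second, if estimates appear only after a significant F, they are on average too large, because trials that happened to observe small differences are filtered out.

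**Working it through.** **Inputs.** From SAP section 2.3: SD 75, target difference 40, two-sided 5%, power 80%, 29 evaluable patients per group in each disease, 25% loss, 117 randomised per disease. From section 2.2: allocation 1:1:1. Assumed, because the SAP gives no figure: the effect of GUT.SUPPORT. It is placed either midway between the other two arms or equal to one of them.

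**The plan's own figure.** n per arm = 2 × (1.960 + 0.842)² × 75² / 40² = 55.2, so 56. The SAP's 29 UC + 29 IBS = 58 per arm agrees with this when the diseases are pooled (power 81.9%). Loss: 29 / 0.75 = 38.7, so 39 per arm and 3 × 39 = 117 per disease. The check therefore uses 58 per arm.

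**Chance that the reporting condition is met.** The F test has 2 and 3 × 58 − 3 = 171 degrees of freedom and noncentrality λ = 58 × Σ(μ − mean)² / 75².

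- Differences from standard care of 40 (GUT.EXPECT) and 20 (GUT.SUPPORT): Σ = 800, λ = 58 × 800 / 5625 = 8.25, P(F significant) = 72%.
- 40 and 0, or 40 and 40: Σ = 1066.7, λ = 11.0, P = 85%.
- 20 and 10: Σ = 200, λ = 2.06, P = 23%.
- No effect: P = 5%.

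**What is reported when the condition is met** (200,000 simulated trials per row, no credit for baseline adjustment):

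| True GUT.EXPECT − SC | GUT.SUPPORT − SC | F significant | Mean estimate given significant F | 95% CI coverage given significant F |
|---|---|---|---|---|
| 40 | 20 | 72% | 46.1 | 96.5% |
| 40 | 0 or 40 | 85% | 43.3 | 96.3% |
| 20 | 10 | 23% | 36.4 | 88.7% |
| 20 | 0 | 29% | 32.9 | 90.7% |
| 0 | 0 | 5% | – | – |

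Averaged over all trials, without selection, the estimate equals the true difference in every row, to within simulation error, and coverage is 95%.

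In the 40/20 case, 10.3% of all trials have GUT.EXPECT versus standard care at p < 0.05 by itself while F is not significant; with GUT.SUPPORT equal to another arm this is 4.1%. The testing rule properly blocks a claim there, but the reporting rule also leaves the estimate without a commitment.

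**What an interval would show after a non-significant F.** Half-width = 1.974 × 75 × √(2/58) = 27.5 points. An observed difference below 40 − 27.5 = 12.5 would exclude the 40-point target; a larger one would not. That information is lost if the interval is omitted.

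**Disease-specific estimates (secondary).** With 29 per cell, suppose the GUT.EXPECT effect differs by 40 points between diseases (for example 60 and 20). The interaction test has 2 and 6 × 29 − 6 = 168 degrees of freedom.

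- GUT.SUPPORT at half the GUT.EXPECT effect: λ = 29 × 400 / 5625 = 2.06, P(p < 0.15) = 42%.
- GUT.SUPPORT without effect: λ = 29 × 533.3 / 5625 = 2.75, P = 50%.

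If the baseline correlation is 0.5 (an assumption; residual variance × 0.75), these become 50% and 59%.

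**The case against.** **The SAP does not say that estimates are withheld.** A reader might infer that a non-significant F means the trial publishes no estimate. The text does not go that far: it makes a promise in one case and is silent in the other. Section 5.4.1 also plans, without any F condition, an adjusted total treatment effect on the 3-month IBS-SSS as part of the mediation analysis. Both points stand, so the finding concerns a missing commitment and not a prohibition. The mediation estimate is no substitute, however: its main model is adjusted for gender and diagnosis, with baseline IBS-SSS entering only in a sensitivity analysis, and its comparator is not spelled out.

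**The size depends on assumptions.** Placing GUT.SUPPORT midway gives the lowest F power for a given GUT.EXPECT difference, which is why the range is shown. Baseline adjustment would also help. If the correlation is 0.5 and 75 is the unadjusted SD, a true 40 gives a significant F in about 85% to 93% of trials, with reported means of 43.2 to 41.4. The 20-point scenario, with its inflation of about 80% (36.4 against 20), is half the design effect and is not an SAP figure; it illustrates direction only.

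**The subgroup rule is weaker ground.** It is tempting to say that the trial's main disease-specific results would usually go unreported. The SAP does not support this. Section 5.4.2 opens with "Exploratory subgroup analyses aim at identifying subgroups which may especially benefit or do not respond well", so these are not main estimates. The sentence stating the rule is garbled, and the interaction p-values themselves are probably reported in any case. A pass rate of 42% to 50% is near a coin toss, not a usual omission. Nor does the rule defeat the aim of learning "whether the same mechanisms of symptom persistence are involved for these two different, yet related diseases": section 5.4.3 compares UC and IBS risk-factor regressions without a significance condition. Asking for a forest plot of every exploratory subgroup would be largely a matter of preference.

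**Conclusion.** The point holds for section 5.2.1. The only commitment to report the primary ANCOVA means, differences and intervals is conditional on a significant F, and the closed-testing argument does not justify that condition. At the design effect of 40 points, about 28% to 15% of trials would leave the powered contrast without a committed estimate, and reported estimates would average 46 to 43 points, an excess of about 15% to 8%. Under no effect about 95% of trials would have no committed estimate. These figures assume SD 75, 58 evaluable per arm, no gain from baseline adjustment and the stated positions of GUT.SUPPORT; a gain from adjustment shrinks the inflation, a smaller true effect increases it. The missing commitment does not depend on any of these assumptions.

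The subgroup limb supports only a secondary suggestion for UC and IBS, because the primary model rests on the absence of a disease-by-treatment interaction and readers need the two estimates to judge that.

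Severity: should-fix. No test, population or sample size is wrong; the defect lies in what the plan undertakes to report.

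**What to change.** In section 5.2.1, replace the reporting sentence with: *Baseline-adjusted means, all three pairwise differences and 95% confidence intervals will be reported regardless of the F test; significance is claimed for a pairwise comparison only if the F test is significant.*

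In section 5.2.2, state whether the same rule applies to the secondary outcomes analysed by ANCOVA.

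Secondary suggestion for section 5.4.2: always report the treatment differences within UC and within IBS with 95% confidence intervals, labelled exploratory, whatever the interaction p-value. With 29 per cell, each has a half-width of about 1.974 × 75 × √(2/29) = 38.9 points before any gain from baseline adjustment, so they should be read as descriptive.

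The cost is a sentence or so in each section and a few more table rows. Tests, sample size and type 1 error stay as they are.

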### 5.2.2 Secondary outcomes

The secondary outcomes will be reported according to their respective scale.

Group differences of PHQ-15, SSCAI, C-reactive protein, and faecal calprotectin will also be analysed using analysis of covariance with underlying disease (UC vs IBS) and sex as additional factors. The same reasoning as for the primary outcome IBS-SSS applies.

All variables will be checked for skewness and if necessary appropriately transformed.

### 5.3 Missing data

If more than 5% of values are missing for the primary outcome, we will use multiple imputation in a sensitivity analysis. The number of imputations for multiple imputation will be chosen depending on the proportion of missing data according to (White, Royston, & Wood, 2011).

### 5.4 Additional analyses

#### 5.4.1 Mediation analysis

In order to analyse whether effects on persistent gastrointestinal symptoms resulted through changes in dysfunctional symptom expectations or illness-related anxiety, we will conduct causal mediation analyses. Mediation analyses will test whether in patients receiving GUT EXPECT, changes in the mediating variables at the 6 weeks' assessment predict a reduction in gastrointestinal symptom severity (IBS-SSS) at 3 months (primary outcome), 6 and 12 months. That is to say, the adjusted total treatment effect (TE) will be divided into the indirect effect, which describes the treatment effect on persistent gastrointestinal symptoms via the mediators, and the direct effect, which describes the treatment effect not mediated through the mediators. Subsequently, the percentage mediated (PM) can be estimated. Only potential mediator-outcome confounders need to be controlled for due to randomisation and a possible treatment-mediator interaction must be considered. To account for mediator-outcome confounding, we adjust generally for gender and diagnosis.

In our main mediation analysis given in Figure 2, we include expectations of symptom severity (EXP 2) and illness-related anxiety (SSD-12) at 6 weeks FU as mediating variables. We use linear structural equation model to estimate the effect of the mediating variables on the IBS-SSS at 3 months and will repeat this analysis, when 6 and 12 month data is available.

The following sensitivity analyses are to be carried out to validate the results and investigate changes in the (in)direct effects and PM with regard to our main mediation model:

- additional adjusting for fecal calprotectin, IBS-SSS at baseline and duration of symptoms and, in a next step, for mediators at baseline (Figure 2)
- include an interaction between the treatment and the mediator(s)
- handling missing values by using the full information maximum likelihood (FIML) approach in the adjusted model with all confounders.

[figure not shown]

Figure 2: Main mediation analysis model

